We will use dual energy x-ray absorptiometry (DXA) scans to measure BMD annually at 3 anatomical sites (lumbar spine, total hip, and wrist). Additionally, we will derive the trabecular bone score (TBS), an index of lumbar spine trabecular microarchitecture.

Hypothesis: Relative to women using DMPA only (without tenofovir exposure) and women using PrEP only (without DMPA exposure), women concurrently using TDF-based PrEP and DMPA will have lower bone mass and more disruptions in bone microarchitecture.

2. We will investigate whether young women concurrently using TDF-based PrEP and DMPA experience: 1) higher rates of bone turnover, a direct precursor to bone loss and 2) subclinical kidney injury and hypoestrogenism, markers of two mechanistic pathways between TDF and DMPA use and bone mass

At baseline, 3, 6, 12, and 24 months, we will measure:

- 1) Markers of bone formation and resorption (e.g. NTX, P1NP, serum intact parathyroid hormone, total and bioavailable 25-OH-vitamin D)
- 2) Markers of kidney function (phosphate, glucose, creatinine, total protein, albumin) and
- 3) Markers of estrogen (serum estradiol, sex hormone binding protein, and the occurrence of amenorrhea)

Hypothesis: Relative to women using DMPA only and PrEP only, women concurrently using TDF-based PrEP and DMPA will have increased bone turnover markers and PTH. In addition, women concurrently using TDF-based PrEP and DMPA will have more frequent subclinical kidney injury (relative to women without tenofovir exposure) and reduced serum estrogen (relative to women without DMPA exposure).

3. Using mediation analysis, we will identify the degree to which the pathways through subclinical kidney injury and hypoestrogenism account for changes in bone density among women concurrently using TDF-based PrEP and DMPA

We will conduct mediation analysis to determine the degree to which changes in the pathways through subclinical kidney injury, hypoestrogenism and the combination of these pathways account for changes in bone density.

Hypothesis: The pathway through hypoestrogenism will be a stronger link between concurrent TDF-based PrEP and DMPA use and bone density changes.

Population

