- Current or recent history of primary or secondary amenorrhea
- Taking medications known to interfere with bone metabolism (steroids, anti-convulsants, bisphosphonates, cancer drugs).
- Has any other condition that would preclude the ability to provide informed consent, make study participation unsafe, complicate the interpretation of study findings or otherwise interfere with achievement of the study objectives, in the investigator's discretion.

Sample size and study power

Power calculations are based on the number of participants needed to achieve aim 1. Our target sample size is 500 women, of which 300 will be using DMPA and 200 will be using condoms for contraception. We calculate that with 300 women newly initiating DMPA and 75% of women choosing to initiate PrEP, thus with 225 women concurrently using PrEP and DMPA and 75 women using DMPA without PrEP, we will have >90% power to detect changes as low as 2.2% in BMD (with 1.0 g/cm² mean BMD loss) at any anatomical site between women using PrEP and DMPA concurrently and women using DMPA only during the 24 month follow up period (Table 4). Should more than 90% of women choose to initiate PrEP (270 women concurrently using PrEP and DMPA and 30 women using DMPA without PrEP), we will have 80% power to detect changes of >2.7% or more and should initiation rates be closer to 50% (150 women concurrently using DMPA and PrEP and 150 women using DMPA without PrEP), we will have >90% power for all comparisons.

Table 4. Power calculations. N=500: 300 on DMPA and 200 on condoms, shown with a range of PrEP acceptance for the primary comparison of DMPA + PrEP vs DMPA ($\alpha=0.05$)

Expected PrEP acceptance	Outcome: BMD (Aim 1)			Outcome: NTX (Aim 2)		
	Mean % Δ (std dev range)	Mean Δ	Power	Mean % Δ	Mean Δ	Power
75% (225 DMPA+PrEP, 75 DMPA)	2.2 (4–5) (0.5–1.0)	0.5 (0.5–1.0)	91%	2.2 (4–5)	0.10 (0.2 – 0.5)	>99%
75% (225 DMPA+PrEP, 75 DMPA)	2.5 (4–5) (0.5–1.0)	0.5 (0.5–1.0)	>96%	2.5 (4–5)	0.20 (0.2 – 0.5)	>96%
75% (225 DMPA+PrEP, 75 DMPA)	3 (4–5) (0.5–1.0)	1.0 (0.5–1.0)	>99%	3 (4–5)	0.50 (0.2 – 0.5)	>99%
90% (270 DMPA+PrEP, 30 PrEP)	2.5 (4–5) (0.5–1.0)	0.5 (0.5–1.0)	74-90%	2.5 (4–5)	0.10 (0.2 – 0.5)	>99%

Recruitment

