Women will initiate contraception at the study clinic or a family planning clinic, as they are seeking services. Throughout study follow up, the study will assume responsibility for contraceptive provision, including DMPA injections, and care of all other methods desired by women. The staff at the IDI-Kasangati research clinic have extensive experience with the provision of contraception and contraceptive counseling during previous HIV prevention studies.

PrEP provision and adherence monitoring

Co-formulated emtricitabine (FTC)-TDF (Truvada®) will be provided as PrEP by the study through donation from Gilead Sciences, LLC. PrEP counseling and provision will follow WHO guidelines, or Ugandan clinical guidelines when they are available.⁶⁰ We will measure adherence using three different methods:

1. Pill counts will be conducted by the pharmacist during study visits to determine the percentage of expected pills that were used
2. Real time monitoring will be conducted using an electronic monitoring system that captures a date-time stamp each time the pill container is opened
3. The primary circulating form of TDF, tenofovir (TFV), will be quantified in blood archives from 1) a random sample of up to 15% of women who initiate PrEP to characterize the adherence in the cohort overall and 2) a targeted group of women who have no BMD change and women who experience a fracture

Laboratory processing to measure markers of bone turnover, subclinical kidney injury, and hypoestrogenism

Using state-of-the-art assay techniques on archival samples, we will measure 1) established markers of bone turnover and bone health, 2) markers of subclinical kidney injury, and 3) markers of hypoestrogenism (Table 5). Archived samples will be batch-analyzed.

Table 5. Measurements for markers of bone turnover, subclinical kidney injury, and hypoestrogenism

Outcome	Biomarkers	Primary Outcome definition	Secondary Outcome definition
Bone turnover and bone health	NTX, P1NP	Percent change from baseline in NTX and P1NP	Percent change from baseline in serum levels of: 
 intact PTH vitamin D binding protein, 25-(OH) vitamin D

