The primary analysis will be separate comparisons of the annualized rates of change in BMD and TBS of the spine and hip between women using PrEP and DMPA concurrently versus women using DMPA only (comparison 1), women using PrEP only (comparison 2), and women using neither (comparison 3). Analyses will account for baseline BMD.

Aim 2, part 1. We will investigate whether young women concurrently using TDF-based PrEP and DMPA experience higher rates of bone turnover relative to women using either agent singly or neither agent

This outcome will be defined by the percent change from baseline of serum levels of NTX and P1NP over 24 months. Secondary outcomes will include: 1) percent change from baseline in serum levels of intact PTH, total 25-(OH)D, bioavailable (i.e. unbound or free) 25-(OH)D calculated from vitamin D binding protein (VDBP) using the standard equation.

$$\text{Free 25(OH)D} = \frac{\text{total 25(OH)D}}{1 + (6 \times 10^3 \times \text{albumin}) + (7 \times 10^8 \times \text{DBP})}$$

To test the hypothesis that combined PrEP and DMPA use is associated with greater bone turnover than DMPA use alone, we will use time-dependent linear mixed-effects regression models to compare mean percent changes in NTX and P1NP between concurrent users of PrEP and DMPA versus users of DMPA only. Secondary powered comparisons will be between: a) concurrent users of PrEP and DMPA versus users of PrEP only; b) users of PrEP only versus users of condoms only; c) users of DMPA only vs users of condoms only. Analysis of the percent change from baseline in serum levels of intact PTH, total 25-OH-D and bioavailable 25-OH-D over 24 months will follow a similar approach. All analyses will be adjusted for confounders and we will consider a broad range of demographic, medical, lifestyle, and sexual behavior characteristics as potential confounders.

Aim 2, part 2. We will investigate whether young women concurrently using TDF-based PrEP and DMPA experience elevated markers of subclinical kidney injury relative to women using TDF-based PrEP alone

This outcome will be defined as having either:

- 1) eGFR decline ($\geq 25\%$ decline from baseline or creatinine clearance $< 60 \text{ mL/min}$). GFR will be calculated using the Chronic Kidney Disease Epidemiology (CKDE) collaboration equation

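### Aim 2 part 1 compares percent change in NTX and P1NP between self-selected groups without naming the baseline marker as a covariate, which leaves the contrast open to baseline imbalance and costs some precision

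*Protocol*

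**What the plan says.** Section V, Aim 2 part 1 defines the outcome: "This outcome will be defined by the percent change from baseline of serum levels of NTX and P1NP over 24 months". Table 5 lists the same primary definition. The model and main contrast follow: "we will use time-dependent linear mixed-effects regression models to compare mean percent changes in NTX and P1NP between concurrent users of PrEP and DMPA" and users of DMPA alone, with three further contrasts described as powered. PTH, total 25(OH)D and bioavailable 25(OH)D are to be handled in a similar way.

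On covariates the text says: "All analyses will be adjusted for confounders and we will consider a broad range of demographic, medical, lifestyle, and sexual behavior characteristics as potential confounders". The baseline level of the marker is neither named nor excluded.

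Two neighbouring passages are more specific. Aim 1, just above, states "Analyses will account for baseline BMD". Aim 2 part 3 names one biomarker to adjust for in the estradiol analysis, the sex hormone-binding protein. The baseline markers are available: under Aims the protocol says of the marker panel "At baseline, 3, 6, 12, and 24 months, we will measure", and the visit table collects blood for archive at enrollment.

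**The concern.** Exposure is not randomised. Every woman is offered PrEP, and the comparison group consists of those who decline. Baseline turnover may therefore differ between the groups, by selection or by chance, and the comparator is small: 75 women at 75% acceptance, 30 at 90%.

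In Aim 2 part 1 the baseline value appears only as the reference that is subtracted and divided by. That does not remove its influence. A woman with a high baseline tends to show a lower percent change later, through regression to the mean, so the group with the higher baseline tends to show the smaller rise whether or not PrEP has an effect. Demographic, lifestyle and behavioural covariates do not reliably absorb this. The same negative correlation leaves explainable variance in the residual. At stake are the validity of the DMPA+PrEP vs DMPA contrast and, secondarily, its precision.

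**Working it through.** **Inputs from the protocol (Sample size section and Table 4).** Alpha 0.05, taken as two-sided because the sidedness is not stated. Groups of 225 vs 75 at 75% acceptance and 270 vs 30 at 90%, no dropout. Percent-scale inputs: differences 2.2, 2.5 and 3 with SD 4 to 5, printed identically for BMD and NTX. NTX differences: 0.10, 0.20 and 0.50 with SD 0.2 to 0.5.

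**Assumptions.** Correlation rho between baseline and follow-up marker of 0.3 to 0.9, and a baseline difference of 0.2 SD between PrEP acceptors and decliners. The protocol gives neither.

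**Step 1: reproduce Table 4.** Power ≈ Φ(d/SE − 1.96), with SE = SD·√(1/n₁ + 1/n₀).
- BMD: 2.2, SD 5, 225 vs 75: SE = 5 × 0.1333 = 0.667 and power 91.0% (printed 91%). 2.5, SD 5: 96.3% (printed >96%). 270 vs 30, 2.5, SD 5 to 4: 73.8% to 90.1% (printed 74-90%). These agree.
- NTX from its own differences: 0.10 at 225 vs 75 gives 96.3% (SD 0.2) down to 32.3% (SD 0.5), printed >99%. 0.20 gives >99.9% down to 85.1%, printed >96%. 0.50 gives >99.9%, printed >99%. 0.10 at 270 vs 30 gives 73.8% down to about 18%, printed >99%.
- NTX from its percent-scale inputs: the second and third rows (>96%, >99%) are reproduced. The first row gives 98.5% to 91.0% and the last 90.1% to 73.8%, so the printed >99% in those two rows follows from neither set of inputs.

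The printed NTX powers therefore cannot show that Aim 2 has precision to spare. The percent-scale inputs are used below as the only coherent set.

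**Step 2: bias from a baseline difference.** Let s be the marker SD, equal at both times. The SD of the change is s·√(2(1 − rho)). If both groups follow the same regression of follow-up on baseline and there is no effect, a baseline difference of 0.2s shifts the mean change by 0.2s(1 − rho). With change SD 5 this equals 0.2 × 5 × √((1 − rho)/2). Dividing by the SE of 0.667 gives the shift in the test statistic.

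| rho | spurious difference (percentage points) | share of 2.2 | shift / SE | false-positive rate |
|---|---|---|---|---|
| 0.3 | 0.59 | 27% | 0.89 | 14% |
| 0.5 | 0.50 | 23% | 0.75 | 12% |
| 0.7 | 0.39 | 18% | 0.58 | 9% |
| 0.9 | 0.22 | 10% | 0.34 | 6% |

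Simulating the same situation gives about 12-14% unadjusted at rho 0.3-0.5 and 6-7% at rho 0.9, against about 5% with the baseline marker in the model. As a yardstick for 0.2 SD, the standard error of a purely chance imbalance is √(1/225 + 1/75) = 0.13 SD at 225 vs 75 and √(1/270 + 1/30) = 0.19 SD at 270 vs 30.

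**Step 3: precision.** Adjustment multiplies the residual variance of the change by (1 + rho)/2, a reduction of (1 − rho)/2: 35%, 25%, 15% and 5% at rho 0.3, 0.5, 0.7 and 0.9.

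| setting | unadjusted | rho 0.3 | 0.5 | 0.7 | 0.9 |
|---|---|---|---|---|---|
| 270 vs 30, 2.5, SD 5 | 73.8% | 89.7% | 85.1% | 80.5% | 76.0% |
| 225 vs 75, 2.2, SD 5 | 91.0% | 98.4% | 96.8% | 94.7% | 92.3% |
| 225 vs 75, 2.2, SD 4 | 98.5% | 99.9% | 99.7% | 99.4% | 98.8% |

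The formula is for a simple change. Simulated true percent changes of a log-normal marker (assumed CV 20% and 40%, 225 vs 75) behave alike: starting power of 74-80% rises to about 87-92% at rho 0.3, 84-87% at 0.5, 83-84% at 0.7 and 81% at 0.9.

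**The case against.** **Silence is not a decision.** A reader might infer that the protocol fixes an analysis without the baseline marker. It does not. The confounder classes are open, a medical characteristic could include a baseline laboratory value, and covariate lists are often completed in a statistical analysis plan, which is not shown here. This stands. What remains is that the protocol does name key baseline or biomarker adjustments for Aim 1 and for estradiol, but not for NTX and P1NP, so its text as written permits the weaker analysis.

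**The aims are not identical.** Aim 1 analyses annualized rates of change and says only that baseline is accounted for, while Aim 2 already scales by baseline. That is true, but scaling does not remove the dependence on baseline, as Step 2 shows.

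**The power figures are borrowed.** A reader might take 74% or 91% as the protocol's expected power for NTX. Those are the powers printed for BMD; the ones printed for NTX are >96% to >99%. Since two of the four NTX entries follow from none of the inputs, and the table may have been damaged in extraction, Table 4 supports no firm statement of lost power in either direction. The study is also sized on Aim 1. In addition, the model is time-dependent with repeated visits, so fixed group sizes and a single follow-up are a simplification.

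**Precision is not free.** In non-randomised groups, adjusting for baseline changes the question as well as the variance. If, without any effect, acceptors and decliners would each keep their own stable mean, the unadjusted change is unbiased and the adjusted one is off by 0.2s − rho × 0.2s = 0.2s(1 − rho), the same size with opposite sign. DMPA may also have begun up to 90 days before enrollment, so the baseline can already reflect exposure. This stands, and is the reason for reporting both models. The primary contrast lies within DMPA users and is less affected by the 90-day window.

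**Conclusion.** The point holds as a gap in the Aim 2 part 1 specification, with a better method available from data already planned. The stronger ground is bias: percent change in self-selected groups carries baseline differences into the contrast. Its size rests on an assumed 0.2 SD imbalance, an assumed rho and a common regression in both groups; on those terms the false-positive rate is about 12-14% at rho 0.3-0.5 and 6-7% at rho 0.9 instead of 5%.

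Lost precision is the secondary ground. It is real at any rho below 1 but depends on a correlation the protocol does not give: 2 to 16 percentage points of power at 270 vs 30 with SD 5, and about 1 point or less at 225 vs 75 with SD 4. The documents do not support saying that Aim 2 is underpowered for this reason, or that the protocol has excluded the covariate.

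**What to change.** Add one sentence to Aim 2 part 1, for example: *The models for NTX and P1NP, and those for PTH and total and bioavailable 25(OH)D, will include the participant's baseline value of the same marker as a covariate; the model without it will be reported as a sensitivity analysis.*

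For contrasts of DMPA users with non-users, show both estimates side by side and say that they can answer different questions, because the baseline sample may follow the start of DMPA.

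The cost is one covariate and one sentence. No new samples or visits are needed. The price is a second set of estimates to interpret where the two models disagree.

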Subclinical kidney injury is characterized by isolated abnormalities in some of markers of kidney function, but without generalized clinical disease manifestation. Kidney toxicity can result in phosphate wasting with hypophosphatemia and secondary hyperparathyroidism, leading to dysregulation of calcium-phosphate homeostasis and bone demineralization.^{24-29, 33} Higher tenofovir plasma concentrations have been associated with higher vitamin D binding protein, lower 1,25-OH(2)D, lower estimated free 25-OHD, and increased parathyroid hormone (PTH) in HIV-infected persons. Vitamin D ensures a proper balance of calcium and phosphorus, key minerals for bone metabolism (Figure 2).^{26, 27}

Our research has recently shown that TDF-based PrEP is associated with a small decline in estimated glomerular filtration rate (eGFR) in African men and women (Table 2).³⁴⁻³⁶ It is not known whether this low level of kidney injury will be exacerbated with prolonged use of TDF-based PrEP or in women with small body mass. Studies are needed to address the effect of

concurrent use of DMPA and TDF-based PrEP on bone acquisition in young women who have generally small body structures that potentially elevate their risk for TDF-induced BMD decline and kidney injury.

Effects of DMPA on bone density

The most commonly used contraception in sub-Saharan Africa is DMPA, used by more than half of contracepting women in Uganda (Figure 3).³⁷

[figure not shown]
⁴⁰ Intramuscular 150mg DMPA is often preferred because of it is easy to administer and can be used discretely. Intramuscular DMPA, as well as a lower dose subcutaneous formulation, is known to yield BMD loss to such an extent as to warrant a “black box” warning from the U.S. Food and Drug Administration.^{38, 41-48} Since 2012, a global partnership of >50 governments, private sector, and multi-lateral organizations has made huge efforts to increase access to subcutaneous DMPA, implying that DMPA will remain the predominant contraceptive in this setting for the foreseeable future.⁴⁸ Women currently using DMPA have a lower average BMD than non-users and these effects are more pronounced in younger women.^{41, 43, 44, 46, 49-51} Longitudinal studies have reported BMD losses up to 7.5% of BMD after ≥ 2 years of use (Table 3) and the greatest amount of loss during the first 1-2 years.⁴⁴

Effects of DMPA on bone metabolism

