Subclinical kidney injury	
 Urine: phosphate, glucose, creatinine, total protein, albumin Serum: phosphate, glucose, creatinine 	eGFR decline calculated using Chronic Kidney Disease Epidemiology equation ($\geq 25\%$ decline from baseline or creatinine clearance $<60 \text{ mL/min}$)	
 Tubular proteinuria: elevated urine protein with urine albumin: protein ratio <0.4, Euglycemic glycosuria, Phosphaturia defined as increased fractional excretion of phosphorus $>15\%$ or maximum rate of tubular phosphate reabsorption to the glomerular filtration rate
Hypoestrogenism	
 Serum estradiol Sex hormone-binding globulin 	Percent change from baseline of serum estradiol with	Frequency of amenorrhea, defined as the absence of menses for at least 3 menstrual cycles

Retention and study exit

Upon completion of study follow up, women will be provided with referrals to clinics of their choice to continue contraceptive and PrEP provision. Since the interim guidelines for HIV prevention now include PrEP, by the time this study is completed, we anticipate that PrEP will be available through public facilities. We will provide participants with information about which facilities are actively providing PrEP and link them to services at that clinic via a referral.

Special circumstances

a. HIV seroconversion

HIV rapid testing will be conducted quarterly during follow up. We expect the rate of HIV seroconversion to be very low, due to the use of PrEP and repeated counseling about HIV prevention and PrEP. However, in the event of HIV positive rapid test results, PrEP will be stopped immediately and additional blood samples will be drawn for confirmatory EIA testing, plasma HIV RNA quantification, drug resistance, and/or drug levels. When with confirmed HIV seroconversion will be extensively counseled and referred to local clinics providing antiretroviral medications and HIV care. At the visit when HIV seroconversion is confirmed, women will be exited from the study once the set of study procedures for an exit visit are completed. HIV seroconverters who are pregnant will be referred for services to prevent mother to child HIV transmission and study staff will go to great lengths to ensure that women experience no delays in accessing these services.

b. Pregnancy

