- 2) proximal tubular injury (tubular proteinuria defined as elevated urine protein with urine albumin-protein ratio < 0.4 , euglycemic glycosuria, phosphaturia defined as increased urinary excretion of phosphorus $> 15\%$ or maximum rate of tubular phosphate reabsorption to the glomerular filtration rate).

These markers were selected because they are routinely available in clinical practice and have been used in prior studies. The cutoff of $\geq 25\%$ for eGFR decline was adapted from established criteria for the diagnosis of acute kidney injury;⁴¹ eGFR decline of this magnitude has been associated with increased morbidity and mortality.²²⁻²⁴

To determine whether young women using PrEP alone or concurrently with DMPA experience higher rates of subclinical kidney injury, we will perform a qualitative comparison of the incidence of individual markers of kidney injury among women using PrEP (alone or concurrently with DMPA) versus women who have no exposure to TDF.

Aim 2, part 3. We will investigate whether young women concurrently using TDF-based PrEP and DMPA experience elevated markers of hypoestrogenism relative to women using DMPA alone

This outcome will be defined as the percent change from baseline serum estradiol over 24 months and we will adjust for sex hormone-binding protein.⁵⁶ The secondary outcome will be based on self-reported missed menses, with > 3 missed menses in a row categorized as amenorrhea.

To determine whether young women concurrently using DMPA alone or concurrently with PrEP experience greater frequency of hypoestrogenism, we will conduct time-dependent logistic

regression among women using DMPA and women not exposed to DMPA, comparing the proportion of visits with hypoestrogenism.

Aim 3. Using mediation analysis, we will identify the degree to which the pathways through subclinical kidney injury and hypoestrogenism account for changes in bone density among women concurrently using TDF-based PrEP and DMPA

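### Table 5's only primary kidney outcome is a yes/no eGFR event that is nearly insensitive to the small mean eGFR decline motivating the aim, so a null eGFR result would not be reassuring

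*Protocol*

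**What the plan says.** - **Motivating effect.** Background, on subclinical kidney injury, reports that "TDF-based PrEP is associated with a small decline in estimated glomerular filtration rate (eGFR) in African men and women". Table 2 puts the net mean difference from placebo in women at -1.73 ml/min/1.73 m² for FTC-TDF and -1.47 for TDF alone. The same section asks whether this low-level injury worsens with longer use or small body mass.
- **Agent.** Section III, PrEP provision: "Co-formulated emtricitabine (FTC)-TDF (Truvada®) will be provided as PrEP by the study".
- **Primary kidney definition.** Table 5: "eGFR decline calculated using Chronic Kidney Disease Epidemiology equation", met by a fall of at least 25% or by creatinine clearance below 60 mL/min. Tubular proteinuria, glycosuria and phosphaturia are in the secondary column.
- **Definition in Section V, Aim 2, part 2.** "This outcome will be defined as having either" the eGFR event (the 25% "decline from baseline or creatinine clearance" below 60) or "proximal tubular injury (tubular proteinuria defined as elevated urine protein with urine albumin-protein ratio" below 0.4, with euglycemic glycosuria and phosphaturia as further signs.
- **Source of the cut-off.** The 25% "for eGFR decline was adapted from established criteria for the diagnosis of acute kidney injury". The protocol adds that a fall of this size has been linked to morbidity and mortality.
- **Analysis.** "we will perform a qualitative comparison of the incidence of individual markers of kidney injury among women using PrEP", against women with no TDF exposure. Change in eGFR as a continuous measure is not a named outcome.
- **Data.** Section III, Aims, plans kidney markers, creatinine among them, at baseline and months 3, 6, 12 and 24.

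**The concern.** The aim is motivated by a mean shift of under 2 ml/min, but its primary measure registers only a loss of a quarter of baseline function or a fall below 60. A shift of the cited size moves very few women across either line. Most eGFR events would then reflect ordinary variation in creatinine, and the groups would probably look alike whether or not PrEP lowers eGFR as cited. In a safety study meant to inform advice on concurrent use, that similarity could be read as evidence of renal safety.

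The choice also stands out within Aim 2. Bone turnover and estradiol are both defined by percent change from baseline. Only the primary kidney outcome is dichotomised.

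**Working it through.** **The plan's own figure.** The protocol states no power for the kidney outcome. Its Table 4 figure for BMD reproduces: a 2.2% difference, SD 5, 225 versus 75 women and two-sided α 0.05 give 91.0%, against 91% stated (SD 4 gives 98.5%). This confirms only the group sizes implied by 75% PrEP uptake.

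**Inputs from the protocol.** Effect 1.73 (Table 2, FTC-TDF); cut-off 25% (Table 5); 500 women; 75% uptake (Sample size and study power).

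**Assumptions, not in the protocol.** Mean baseline eGFR 110–140; SD of within-woman change 10–15; 75% uptake in both contraceptive groups, giving 375 on PrEP and 125 with no TDF; a uniform shift; no mean change without TDF; normal changes; correlation between visits 0.3–0.7 for the continuous analysis.

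**Step 1, cut-off against effect.**
- 0.25 × 110 = 27.5; 27.5 / 1.73 = 15.9
- 0.25 × 140 = 35.0; 35.0 / 1.73 = 20.2
- At a baseline of 90 the ratio is 22.5 / 1.73 = 13.0; at 150 it is 37.5 / 1.73 = 21.7. It stays above ten throughout.

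**Step 2, share crossing 25%.** At one visit, q0 = Φ(−0.25·baseline/SD) and q1 = Φ((−0.25·baseline + 1.73)/SD). At any of four visits taken as independent, p = 1 − (1 − q)⁴. Power is for a two-sided two-proportion normal test, 375 versus 125.

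| Baseline, SD | One visit, no TDF → PrEP | Any of four visits | Expected any-visit events, PrEP / no TDF | Power |
|---|---|---|---|---|
| 110, 10 | 0.30% → 0.50% | 1.2% → 2.0% | 7.4 / 1.5 | 6% |
| 110, 15 | 3.3% → 4.3% | 12.7% → 16.1% | 60.3 / 15.9 | 14% |
| 140, 10 | 0.02% → 0.04% | 0.1% → 0.2% | 0.7 / 0.1 | 3% |
| 140, 15 | 1.0% → 1.3% | 3.9% → 5.2% | 19.5 / 4.8 | 7% |

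Independence between visits favours the cut-off. On a single visit, power in these scenarios is about 1.5–5.6%. Where events are very few the normal approximation is crude.

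**Step 3, the below-60 criterion.** From a mean of 110, reaching 60 takes a loss of 50; from 140, a loss of 80. Only women already close to 60 could cross on a shift of 1.73.

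**Step 4, continuous change from the same four samples.** SE = SD × √((1 + 3ρ)/4) × √(1/375 + 1/125), where the last factor is 0.1033.
- SD 10, ρ 0.3: SE = 10 × 0.689 × 0.1033 = 0.712; CI half-width 1.96 × 0.712 = 1.4; power Φ(1.73/0.712 − 1.96) = 68%
- SD 15, ρ 0.7: SE = 15 × 0.880 × 0.1033 = 1.364; CI half-width 2.7; power Φ(1.73/1.364 − 1.96) = 24%

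**Step 5, an effect twice as large (3.46).** On the same assumptions the cut-off has about 2–45% power, and continuous change 72% to above 99%.

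**The case against.** **The outcome is wider than eGFR.** A reader might infer that Aim 2, part 2 as a whole cannot detect subclinical injury. The protocol does not support that. Section V also counts proximal tubular injury and compares markers individually. Those markers do not depend on the 25% cut-off, and they fit the Background's description of subclinical injury as isolated marker abnormalities. The point is confined to the eGFR component. That component is still the only primary kidney definition in Table 5.

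**The cut-off has a clinical rationale.** The link to morbidity and mortality is stated, and a mean effect and an individual threshold are different quantities. A susceptible minority could lose 25% while the mean hardly moves, and the calculations assume a uniform shift. This stands, and is why the event should be kept.

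**No test is planned.** Section V specifies a qualitative comparison, so the power figures only gauge how far the event responds to a shift. Comparing such similar proportions by eye is no more sensitive.

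**The aim is not to show 1.73 again.** The Background asks whether the decline is exacerbated. Step 5 shows that the cut-off responds weakly even to a doubled shift.

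**Aim 3.** One might infer that the kidney pathway in the mediation analysis will look falsely weak. Section V, Aim 3 allows creatinine and other individual markers to define that pathway, so this does not follow.

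**The analysis plan may add it.** A continuous analysis could be in an SAP that is not shown. The protocol itself, however, fixes the yes/no primary definition and names the comparison.

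**Conclusion.** The concern holds for the eGFR component. For FTC-TDF, the 25% cut-off is about 16–20 times the cited mean effect if baseline eGFR is 110–140, and about 13–22 times across 90–150. A multiple of 24 might be tempting, but it needs the TDF-alone effect (35 / 1.47 = 23.8), and TDF alone is not the supplied agent. It would also be wrong to say that only 25% falls count, because creatinine clearance below 60 counts too; that criterion is just as unresponsive to a small shift.

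Under the stated assumptions, a test on the event would have about 3–14% power for a shift of 1.73, against about 24–68% for continuous change. A null eGFR result would therefore say little about a decline of the cited size. The ratio alone does not prove non-detection, and large falls in a minority could still appear.

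Separately, Table 5 makes the tubular markers secondary while Section V makes them an equal route to the outcome. These two definitions need reconciling.

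**What to change.** In Table 5 and Section V, Aim 2, part 2:

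1. Add change from baseline in CKD-EPI eGFR. Use a mixed model over months 3, 6, 12 and 24, adjusted for baseline eGFR and confounders. Estimate PrEP versus no TDF, and PrEP with DMPA versus PrEP alone (the contrast in the heading of part 2). Report each difference with a 95% CI, and show the cited 1.73 beside the first.
2. Keep the 25% or below-60 event as a descriptive safety outcome. Do not require confirmation in the next sample: some of those samples have no planned assay, and month 24 has no later sample.
3. Reconcile Table 5 with the either/or definition in Section V, so that the status of the tubular markers is the same in both.

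**Cost.** Protocol wording and one more analysis; the samples and creatinine assays are already planned. The added analysis is still only modestly powered for 1.73, with a CI half-width of about 1.4–2.7 ml/min for PrEP versus no TDF. For PrEP with DMPA versus PrEP alone (225 versus 150 at 75% uptake) the last factor in the SE is √(1/225 + 1/150) = 0.1054, so precision is similar. Its value lies in an estimate with a stated uncertainty, which a qualitative count of events does not give.
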